The purpose of a RBC transfusion is to increase tissue oxygenation, thereby reducing tissue oxygen debt. During storage progressive morphological and biochemical changes occur to the RBC product which may contribute to a reduction in microvascular tissue flow and contribute to tissue hypoxia. ¹⁹⁻²³ The observed increase in complications in transfused patients could be related, in part, to older RBC units contributing to reductions in local tissue oxygenation. After RBC transfusion, an increase of hemoglobin levels is readily observed, but the effect of RBC transfusion on tissue oxygenation is rarely measured. Therefore, a quantitative evaluation of the effectiveness of stored RBC in increasing tissue oxygenation is required to assess the risk of complications related to tissue oxygenation and storage duration of the RBC units transfused.

B. Background and Significance:

Effect of RBC Storage Time

Considerable evidence suggests that transfusions increase the risk of serious complications and mortality in both cardiac surgical patients²⁴⁻³¹ and in critically ill patients.³²⁻³⁴ But evidence also suggests that, within the transfused population, risk of complications increases when administered blood has been stored for long periods of time.^{5, 6, 9, 15, 35} Blood banks, including ours, generally provide clinicians with the oldest matched units to minimize the number that expire. Under American Red Cross guidelines, packed red cells can be stored up to 42 days. It is well established that storage provokes a progressive degradation in erythrocyte shape and deformability, beginning after about two weeks.^{1, 2, 17, 18} However, the clinical importance of transfusing older versus younger red cells remains unclear with some studies identifying adverse consequences^{5, 6, 9, 15, 35} and others not.^{12, 16, 36, 37} Raat and colleagues¹⁹ reported that among 74,084 units of RBC transfused, more than one-third were units transfused with storage durations greater than 3 weeks. Among patients with type AB negative, up to 68.4% of units transfused were greater than 3 weeks storage duration.¹⁹

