From preliminary data on approximately 6000 cardiac surgical patients in our institution, we report that increasing RBC storage duration is associated with increased risk for morbid outcomes following cardiac surgery. Hospital death, intubation morbidity, renal failure, sepsis, multisystem organ failure and composite outcome were higher in the group with increasing RBC storage duration. We are also aware of the strong and incrementally increased risk for morbid outcomes associated with each unit of RBC transfused²⁴⁻²⁶.

C. Preliminary Studies

Recent work⁴⁶ from our institution demonstrated a significant risk-adjusted impact of RBC transfusion on in-hospital mortality, pulmonary, cardiac, renal, infectious and neurological morbidity in over 11,963 isolated CABG patients. Transfusion was the single factor most reliably associated with increased risk for these morbid events. Figure 1 displays the unadjusted relationship between units of RBC transfused, platelet transfusion and morbidity and mortality outcomes. As the number of units of RBC transfused is increased, so is the risk for every postoperative adverse outcome. Figure 2 displays a Forrest plot of unadjusted and adjusted odds ratios and their confidence limits for the seven postoperative morbid outcomes.

[figure not shown]

In a separate investigation²⁵, we demonstrated the association between RBC transfusion and an increased early (within 6 months after surgery) and late hazard (out to 10 years) for death. We examined the incremental influence of perioperative RBC transfusion and component therapy on long-term survival after isolated coronary artery bypass grafting after controlling for the effects of demographics, comorbidity, operative factors and the early hazard for death. Approximately half of the 10,289 patients received at least 1 unit of RBC in the perioperative period. Survival among transfused patients was significantly reduced compared to those who did not receive a RBC transfusion. Figure 3. The hazard for death displayed a more influential early impact of RBC transfusion out to 6 months postoperatively. While the late hazard for death was less, the association was remained statistically significantly different from those who did not receive RBC transfusion throughout the follow-up period. Risk-adjusted reduction in survival for both early and late phases were (0.34 +/- 0.02, P <0.0001) and late phases (0.074 +/- 0.016, P <0.0001).

Figure 3.

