This trial is a single center, two-arm parallel design with two interventions: newer blood versus older blood. Patients randomized to the newer blood group will receive blood units that have been stored less than or equal to 14 days; patients randomized to the older blood group will receive blood units that have been stored more than or equal to 20 days. The primary outcome is a binary composite outcome composed of major and minor postoperative morbid events defined by STS definitions. The secondary outcomes include prolonged postoperative ventilation and occurrence of atrial fibrillation, length of intensive care unit and length of hospital stay. These outcomes will be assessed by research assistants blinded to the treatment assignment. All the outcomes are short-term endpoints that can be ascertained within a few weeks after the operation, which makes it possible to do sequential monitoring. The randomized groups will be descriptively compared on all baseline variables using summary statistics such as mean and standard deviation, median and quartiles or frequency and percent, as appropriate. No two-sample tests on baseline variables are necessary, but those that are believed to be strongly correlated with the outcomes will be included in the covariate adjustment in the primary and secondary analyses. The level of statistical significance used in the primary analysis will be 0.05, and all tests in the primary and secondary analyses are two-tailed. The statistical analysis will be performed using SAS 9.1 (SAS Institute, Cary, NC).

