If a patient meets the inclusion criteria and gives consent, he/she could potentially be randomized in the trial. Before the start of surgery, the research coordinator responsible for randomization will check the randomization list and determine that person's randomization allocation. The coordinator will then contact the blood bank and check whether there are adequate type-matched newer or older blood units available for that patient. Occasionally, there is short of supply of newer or older blood for a certain blood type. If the Blood Bank can not ensure that the patient receive only the kind of blood he/she is randomized to receive, that patient will be taken out of the trial and not randomized. We expect that this failure of randomization occurs infrequently, and it more likely occurs to patients with rare blood types. Since there is no evidence for an interaction between rare blood types and age of blood, this practice is not expected to introduce bias to the study. Another situation that may cause failure of randomization is that the patient may not need any transfusion for the entire hospital stay as determined by the surgeon. In that case the patient will also be taken out of the trial at hospital discharge. We expect that about 40-50% patients will not need any transfusion. This is a special kind of drop-out after randomization. However, since the dropping out is not related to the treatment assignment, we do not believe it will introduce bias to the study, and the two treatment arms will still be balanced.

The primary analysis is a two-sided chi-square test comparing the two treatment groups on the rate of composite outcome, based on the intent-to-treat (ITT) principal. The 95% confidence interval of the rate of

composite outcome will be calculated for the two treatment groups, and for the treatment effect which is quantified by the odds ratio.

We will test the interaction between the treatment groups and the recipients' blood type, and donors' blood type. In this way, we may identify subgroups more sensitive to the treatment. Although pre-specified, we will interpret the estimated interactions and their statistical significance with much caution due to multiplicity and they are not the primary analysis or focus. Our assessment of interactions will be viewed as exploratory and hypothesis generating.

Sample Size Calculation and Sequential Monitoring

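### Allocation is read before the blood supply is checked, so removal for shortage depends on the assigned arm, and the plan's no-interaction argument does not address this

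*Combined protocol and SAP*

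**What the plan says.** The procedure is in the randomization paragraph of the Statistical Analysis Plan. It has three steps, in this order.

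1. Before surgery, "the research coordinator responsible for randomization will check the randomization list and determine" the patient's allocation.
2. "The coordinator will then contact the blood bank and check whether there are adequate type-matched newer or older blood units available for that patient".
3. Where the blood bank cannot guarantee "only the kind of blood he/she is randomized to receive, that patient will be taken out of the trial and not randomized".

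The plan gives two reassurances. On frequency: "We expect that this failure of randomization occurs infrequently, and it more likely occurs to patients with rare blood types". On bias: "Since there is no evidence for an interaction between rare blood types and age of blood, this practice is not expected to introduce bias". The same paragraph also says that dropping out is unrelated to treatment assignment, but that sentence is about patients who turn out to need no transfusion, not about supply failures.

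The primary analysis is a two-sided chi-square test, described as intention-to-treat. Baseline variables are to be compared descriptively, and "those that are believed to be strongly correlated with the outcomes will be included in the covariate adjustment in the primary and secondary analyses". The plan does not ask for supply removals to be counted by arm.

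**The concern.** The arm is known when the decision to keep or remove the patient is made, and the decision turns on stock of the assigned kind of blood. The two analysed groups are then no longer simply the two halves of a random split. Calling a patient whose allocation has been read not randomized also takes that patient out of an analysis labelled intention-to-treat.

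Two conditions must both hold for this to bias the comparison.

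- **Shortage must differ between arms.** Section B (Background and Significance) makes this plausible for rare types. In an outside cohort more than one-third of all units were over three weeks old, but "Among patients with type AB negative, up to 68.4% of units transfused were greater than 3 weeks storage duration".
- **Removed patients must differ in risk.** Supply has to be adequate for the individual patient, so expected transfusion need may enter. Section B describes a "strong and incrementally increased risk for morbid outcomes associated with each unit of RBC transfused". This link is an inference; the plan itself names only blood type as a driver of removal.

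The direction cannot be predicted, because the plan says either kind of blood may run short. Losing higher-risk patients from the newer-blood arm would make older blood look worse than it is. Losing them from the older-blood arm would hide a real effect.

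**Working it through.** **Does the stated defence cover the problem?** An interaction concerns whether the effect of storage age differs between blood types. Selection bias concerns whether the patients kept in each arm remain comparable. The calculations below contain no interaction at all, and bias still appears whenever removal is one-sided and related to risk.

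**Inputs from the plan** (Sample Size Calculation and Sequential Monitoring): overall event rate about 30%; 27.3% versus 32.7% under the alternative; two-sided alpha 0.05; power 0.85; 1328 per arm for a fixed design; maximum 2838, or 1419 per arm.

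**Assumed inputs:** the fraction f of one arm removed (1%, 2%, 5%) and the event rate q among those removed (30% to 60%). The plan gives neither.

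**Plan's own figure.** The continuity-corrected two-proportion formula at 27.3% versus 32.7% gives 1329 per arm, 2658 in total, against the stated 2656. It reproduces.

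**No true effect.** The event rate left in the depleted arm is (p − f·q)/(1 − f), with p = 0.30. For f = 0.05 and q = 0.50 this is (0.30 − 0.025)/0.95 = 0.2895. The spurious odds ratio is (0.30/0.70)/(0.2895/0.7105) = 1.05. Type I error is from one pooled two-proportion z test with 1419 per arm, ignoring the interim looks.

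| Event rate in removed patients | f = 1% | f = 2% | f = 5% |
|---|---|---|---|
| 30% (unrelated to risk) | 5.0% | 5.0% | 5.0% |
| 40% | 5.0% | 5.2% | 6.1% |
| 50% | 5.2% (OR 1.01) | 5.6% (OR 1.02) | 9.4% (OR 1.05) |
| 60% | 5.4% | 6.5% | 15.2% |

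Shortages in both arms offset each other. With q = 50%, losing 5% from one arm and 2.5% from the other gives an odds ratio of 1.03 and a type I error of about 6%. Equal losses give 5.0%.

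**Planned effect present, older-blood arm depleted, q = 50%.** The older-arm rate becomes (0.327 − f × 0.50)/(1 − f). Power is for the fixed test with 1328 per arm, without continuity correction, so it starts slightly above the plan's 85%.

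| f | Older-arm rate | Odds ratio | Power |
|---|---|---|---|
| 0 | 32.7% | 1.29 | 86% |
| 1% | 32.5% | 1.28 | 84% |
| 2% | 32.3% | 1.27 | 81% |
| 5% | 31.8% | 1.24 | 72% |

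**Existing safeguards.** Baseline comparison and covariate adjustment act on measured differences among patients who stay in. They do not restore removed patients. The baseline lists in Appendix 1 omit blood type, the one factor the plan ties to removal.

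**The case against.** The strongest reply is that the second condition is not documented. Blood type is the only stated driver of removal, and nothing in the plan links blood type to outcome. If it is unrelated to risk, the 30% row applies and there is no bias. Section C (Preliminary Studies) adds that the blood bank at this centre was blinded to clinical status when it assigned units by age, and that most patient characteristics were evenly distributed. The larger figures above also need three things at once: 5% removal, all from one arm, in patients at much higher risk. The plan expects failures to be rare and says either kind may run short. The AB negative figure is a maximum for transfused units in an outside cohort, not stock at this centre.

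Much of this stands as a limit on size. It does not rescue the procedure. The preliminary data concern units issued in an observational cohort, not patients refused for lack of stock. Rarity is asserted, and without counts by arm no reader could confirm it.

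A further fair point is that the plan intends to test an interaction with recipient blood type, so blood type must be recorded somewhere for analysed patients. Adding it to Appendix 1 is therefore tidying. The interaction test still neither counts removed patients nor corrects removal that depends on the arm.

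**Conclusion.** The concern holds. Removal for supply reasons depends on the assigned arm by rule, and the absence of an interaction is not the condition that would make this harmless. Confidence is high on the order of steps and on the justification, and low on the size.

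The bias is nil if removed patients have average risk or if losses are equal in both arms. At 1–2% removal, which seems a fair reading of a rare event, type I error stays between 5.0% and 6.5% across assumed event rates of 30% to 60%. It becomes material at about 5% one-sided removal of higher-risk patients. All of these figures rest on assumed removal rates and risks. The case for change rests on the avoidable flaw in procedure and the missing reporting more than on the 5% scenarios. It should be fixed.

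**What to change.** In the randomization paragraph of the Statistical Analysis Plan:

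- Reverse the order. The blood bank confirms adequate type-matched stock for both arms before the allocation is opened, and the patient is randomized only if both are available.
- Once the allocation is opened, count the patient as randomized and do not remove the patient from the trial for supply reasons. Report any supply failure by arm.
- Delete the no-interaction justification.
- Add recipient blood type to the baseline list in Appendix 1, so that the descriptive comparison covers it.

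Supply exclusion then cannot depend on the arm, and the planned 2838 is unchanged.

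**Cost.** Protocol wording, one case report form line, and the same call to the blood bank asking about two inventories. A few more patients, mainly with rare blood types, will not be randomized. With 40–50% untransfused, reaching 2838 transfused patients needs 2838/0.60 = 4730 to 2838/0.50 = 5676 randomized. If one arm is short for a fraction f of candidates, the present rule loses about f/2 of them and the new rule loses f. The extra consenting patients are therefore that number × [1/(1 − f) − 1/(1 − f/2)]: about 24–29, 49–59 or 128–153 for f = 1%, 2% or 5% (assumed). A shortage that arises after allocation would leave some patients with off-arm units in the intention-to-treat set, which dilutes the contrast somewhat; reporting by arm makes this visible.

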**Red Cell Storage Duration and Outcomes in Cardiac Surgery:
A Randomized Controlled Trial**

[name] [name], MS, FACC and Colleagues
Departments of Cardiothoracic Anesthesia and Outcomes Research

NCT 00458783

Cleveland Clinic
[name]
[name]

[contact]
[contact]
E-mail: [contact]

Currently RBC units that have been stored up to 42 days are available for transfusion. Increasing RBC storage duration has been shown to alter red cells by reducing oxygen availability, creating proinflammatory and immunomodulatory effects, as well as reducing red cell deformability, and aggregability. Prior observational investigations report variable results in terms of morbid outcomes related to increasing length of RBC storage. We propose a randomized blinded clinical trial with a maximum enrollment of 2840 adult cardiac surgical patients. Consecutive consenting patients who meet the inclusion criteria will be randomized to 'age of blood' less than two weeks or greater than 20 days shelf life for all of the units allocated to the patient. The trial uses a group sequential design with three internal interim analyses that examine group sequential boundaries of both efficacy and futility. The overall type I error rate is 0.05 and power is 85%. The study we propose will provide an appropriate level of evidence for determining whether increased storage duration is associated with increased morbidity. We estimate that it will take approximately 2-3 years to complete the enrollment and randomization.

Personnel

Name	Organization	Role on Project
[name] [name], MS	CCLMC-CWRU*	Principal Investigator
[name]	CCLMC-CWRU	Co-investigator,
[name]	CCLMC-CWRU	Co-investigator,
[name]	CCLMC-CWRU	Principal statistician
[name]	CCLMC-CWRU	Co-investigator, Cardiothoracic anesthesiologist
[name]	CCLMC-CWRU	Co-investigator, Cardiothoracic anesthesiologist
[name]	CCLMC-CWRU	Co-investigator, cardiothoracic surgeon
[name]	CCLMC-CWRU	Co-investigator, cardiothoracic surgeon
[name]	CCLMC-CWRU	Co-investigator, cardiothoracic surgeon
[name]	CCLMC-CWRU	Co-investigator, cardiothoracic surgeon
[name]	CCLMC-CWRU	Co-investigator, Laboratory medicine/ Clinical pathology
[name]	CCLMC-CWRU	Co-investigator, Laboratory medicine/ Clinical pathology

*Cleveland Clinic Lerner College of Medicine, Case Western Reserve University

Executive Committee

Name	Role
[name], MS	Chair
[name]	Member
[name]	Member
[name]	Statistician, non-voting

A. Specific Aims

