Cleveland Clinic Heart Center is a large tertiary care center and is among the busiest cardiac surgical centers in the US. Our annual volume over the last 5 years for coronary artery bypass grafting, and valve procedures has been between 3500-3790 surgeries. Transfusion of RBC currently occurs in approximately 40-50% of these patients.

Inclusion Criteria

All primary and reoperative adult cardiac surgical patients undergoing cardiopulmonary bypass for coronary artery bypass grafting, coronary artery bypass grafting with a valve procedure, isolated valve procedures and ascending aortic aneurysm or dissection repair alone or combined with CABG and valve procedures.

Exclusion criteria:

Age less than 18 years, descending thoracic aortic aneurysm repairs, left or right ventricular assist devices, and those unwilling to receive blood for religious reasons (Jehovah Witness).

Protocol

Our primary aim is to determine whether increased length of storage of RBC is related to adverse perioperative outcomes.

Study Intervention

Consecutive consenting patients who meet the inclusion criteria will be randomized to 'age of blood' less than two weeks or greater than 20 days shelf life for all of the units allocated to the patient. Red blood cell and component transfusion will follow management decisions of the care team. Adherence to the treatment protocol will be required for the patients in the operating room, intensive care unit and postoperatively until discharge from the hospital. Good clinical judgment supersedes the protocol.

Measurements

Baseline Information:

Baseline demographics, laboratory values, comorbidity, surgical procedure, operative variables, and postoperative morbid events are contained in Appendix 1. (CRF). These variables are routinely prospectively collected by the Departments of Cardiothoracic Anesthesia and Thoracic and Cardiovascular Surgery Cardiovascular Information Registries. These research registries have been approved by the institutional Internal Review Board for research purposes. Individual patient consent has been waived. Anesthesia automated record keeping system (ARKS) currently stores all hemodynamic information, intraoperative medication usage, arterial blood gas analyses, amount of crystalloid administered, time, number and identification number for RBC units transfused. Component blood product use and urine output are also automatically recorded and stored within the automated system.

Primary Outcome

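### The arm is read from the randomization list while the patient can still be taken out, and no method of allocation concealment is stated

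*Combined protocol and SAP*

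**What the plan says.** The procedure is in the Statistical Analysis Plan, in the paragraph that begins with eligibility and consent. It has four steps.

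1. Eligibility and consent come first: "If a patient meets the inclusion criteria and gives consent, he/she could potentially be randomized in the trial".
2. Before surgery, "the research coordinator responsible for randomization will check the randomization list" and reads off the patient's arm.
3. The supply check follows: "The coordinator will then contact the blood bank and check whether there are adequate type-matched newer or older blood units available for that patient".
4. If the blood bank cannot guarantee the kind of blood assigned, "that patient will be taken out of the trial and not randomized".

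On how often step 4 occurs, the plan says only "We expect that this failure of randomization occurs infrequently". It argues that these removals cause no bias because nothing suggests that rare blood types interact with the age of blood.

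Two other statements bear on the point. The Study Intervention section says "Consecutive consenting patients who meet the inclusion criteria will be randomized". The opening summary says "We propose a randomized blinded clinical trial with a maximum enrollment of 2840 adult cardiac surgical patients", and the Statistical Analysis Plan adds that outcome assessors are blinded.

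**The concern.** Randomization protects against selection only if nobody who can influence entry knows the assignment when entry is settled. Here the arm is known at step 2 and entry is settled at step 4. A removal at step 4 is thus made with the arm known, on a question that itself depends on the arm (is there enough of the assigned kind?). The removed patient is then classed as never randomized, so falls outside the intent-to-treat set. No log of removals by arm is required, which would make an imbalance in removals hard to see afterwards.

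The investigators' own preliminary data, in Preliminary Studies, associate longer storage with worse outcomes. Staff may therefore have a view on which arm suits a sick patient. The primary test is a chi-square comparison of event rates. The covariate adjustment mentioned elsewhere in the plan could correct only for risk that was measured.

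**Working it through.** **The text.** I looked through the combined document for any concealment step. It mentions no sealed envelopes, no telephone or web release, no independent holder of the list and no one-at-a-time release. It does not say who generates the list, whether blocks or strata are used, or what happens to the list entry of a removed patient. The statements on blinding concern what is known after assignment and at outcome assessment, not before entry. The argument about rare blood types concerns which patients lack supply, not who knows the arm when they are removed.

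**The plan's own figure.** Inputs from Sample Size Calculation: 27.3% against 32.7%, two-sided 0.05, power 0.85, equal allocation.

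- n = [1.960 × √(2 × 0.30 × 0.70) + 1.036 × √(0.273 × 0.727 + 0.327 × 0.673)]² / 0.054² = 1292 per arm.
- With the continuity correction this becomes 1329, against the stated 1328.

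The figure reproduces, and this point does not affect it.

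**How many assignments reuse would expose.** The plan gives no removal rate, so I assume q = 1%, 5% or 10%, and assume that a removed patient's entry passes to the next patient. With 40–50% not transfused, 2838 transfused patients need 2838/0.60 = 4730 to 2838/0.50 = 5676 randomized. Look-ups are that number divided by (1 − q); exposed assignments are q times the look-ups.

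| q | exposed | of these, transfused: 2838q/(1 − q) |
|---|---|---|
| 1% | 48–57 | 29 |
| 5% | 249–299 | 149 |
| 10% | 526–631 | 315 |

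**What foreknowledge could do.** Suppose a share f of assignments is foreknown, and selection shifts baseline risk between arms by r = 5 points among them. Take 1419 per arm, a 30% event rate, no true effect and a single two-sided 0.05 test. The standard error is √(2 × 0.30 × 0.70/1419) = 0.0172. The error is Φ(−1.96 + f·r/0.0172) + Φ(−1.96 − f·r/0.0172).

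| f | type I error |
|---|---|
| 5% | 0.052 |
| 10% | 0.060 |
| 25% | 0.112 |
| 100% | 0.83 |

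**Selective non-entry in one arm.** Assume a 30% event rate, no true effect, and a fraction s of patients with a 60% event rate not entered in one arm only. That arm's rate becomes (0.30 − 0.60s)/(1 − s). The rejection probability uses the four looks and the thresholds of the plan's Table 1 on stopping boundaries.

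| s | depleted arm | false difference | error, futility not enforced | error, futility followed |
|---|---|---|---|---|
| 0 | 30.0% | 0 | 5.0% | – |
| 2% | 29.4% | 0.61 points | 6.4% | 5.9% |
| 3% | 29.1% | 0.93 points | 8.3% | 7.6% |
| 5% | 28.4% | 1.58 points | 14.9% | 13.7% |

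The design difference is 32.7 − 27.3 = 5.4 points.

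**The case against.** The best reply is that the plan is merely brief. It describes a look-up for one person, after eligibility and consent, in consecutive patients. The supply judgment belongs to the blood bank. The coordinator is not said to recruit or obtain consent. Baseline variables will be compared by arm, and quarterly external audits are planned.

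Much of this stands, and it rules out several stronger readings that a reader might infer:

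- **That the coordinator sees later assignments.** The text does not say that the list is open beyond the current line. A list revealed one line at a time is not excluded.
- **That a removed patient's entry goes to the next patient.** The plan is silent. Even if it were so, rare removals alone would matter little: about 5.2% to 6.0% error when 5–10% of assignments are foreknown.
- **That the wording in step 1 gives the coordinator discretion over entry.** In context it introduces two named reasons for leaving the trial: lack of supply and no need for transfusion.
- **That the true error rate is near 15%.** At s = 5%, about 0.05 × 1419 = 71 patients at double the base risk would have to be correctly identified and withheld from the same arm. More would have to be withheld in practice, since some entrants are never transfused. Nothing in the documents supports such a rate.

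What does not stand is the claim that only detail is missing. The stated order itself puts knowledge of the arm before the final decision on entry, and the stated rule then erases the removed patient from the randomized set. Consecutive enrolment and prior consent do not alter that order. Baseline comparison can reveal only selection on measured risk.

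**Conclusion.** The point holds as a flaw in a stated procedure. The current patient's arm is known while that patient can still be taken out, removal leaves the patient classed as not randomized, and no concealment step is described. Whether later assignments can also be foreseen depends on two things that the documents leave open: how much of the list is visible, and whether entries are reused.

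The documents give no basis for a numerical estimate of bias, and they do not show that any selection took place. The error rates above rest wholly on assumed values of q, f, r, s and the 60% event rate. They show that a few exposed assignments would do little harm and that an openly readable list could do much more. The point merits a change to the procedure. It does not show that the trial's error rate is wrong.

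**What to change.** Rewrite the randomization paragraph to state the following.

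- **Holder.** The list is generated and held by someone with no role in enrolment or supply decisions, such as the statistical group or a simple computer release. Blood bank staff who judge supply should not hold it, because their judgment decides who is removed.
- **Order.** One assignment is released at a time, and only after eligibility, consent, identity and supply of both kinds of blood are confirmed.
- **Accounting.** Every released assignment is logged by arm, counted as randomized and never reused. This replaces the present rule that unsupplied patients were not randomized. The plan's separate handling of patients who are never transfused is outside this point.

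The cost is one extra step and one log entry per patient. A patient for whom either kind of blood is lacking is excluded before assignment, so somewhat more patients may be excluded than when only the assigned kind is checked, but the exclusion no longer depends on the arm. If concealment of this kind is already practised, the holder and release steps need only be written down.
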